12.2 Auditing

The Sponsor may conduct audits at the study center(s). Audits will include, but not be limited to, investigational product supply, presence of required documents, the informed consent process, and comparison of eCRFs with source documents. The investigator agrees to permit audits conducted at a reasonable time in a reasonable manner.

Regulatory authorities worldwide may also inspect the investigator during or after the study. The investigator should contact the Sponsor immediately if this occurs, and must permit regulatory authority inspections.

12.3 Protocol Deviations

Deviations from the protocol identified during the conduct of the trial will be recorded in the eCRF. These include but are not limited to the following:

- Inclusion criteria violation
- Exclusion criteria violation
- Laboratory assessments not drawn at Day 1, Day 150, 510 or Day 720 (EOS) visits
- Mis-Dosing for any reason other than subject safety or withdrawal (defined as missing dose or a dose delayed by more than 30 days)*
- Subject taking any prohibited concomitant medication
- Change in baseline statin or other lipid-lowering therapy dose
- SAEs not reported to the Sponsor within 24 hours
- Informed Consent not signed prior to study entry

*If the mis-dosing was unintended, ie, a medication error, the error should be reported as per instructions in [Section 8.4.3.1, Medication Errors](#).

Additional protocol deviations and associated actions depending on the nature and impact of the protocol deviation will be defined and periodically reviewed by standard automated and/or manual checks by the clinical team or monitors.

13 Ethics and Responsibility

This study will be conducted in compliance with the protocol, the Sponsor's standard operating procedures and/or guidelines, the US FDA regulations, the ICH GCP guidelines, the Declaration of Helsinki and other local regulations, as applicable.

13.1 Informed Consent

Written informed consent will be obtained from all subjects (or their guardian or legally authorized representative), and whenever possible, or as per IRB or EC guidelines before any study-related procedures (including any pre-treatment procedures) are performed. The investigator(s) has both ethical and legal responsibility to ensure that each subject (and their guardian or legally authorized representative) being considered for inclusion in this study is given a full explanation of the protocol. This shall be documented on a written informed consent form, which shall be approved by the same IRB or EC responsible for approval of this protocol. Each informed consent form shall include the elements required by ICH, Part E6, Section 4.8 and any applicable local regulations. The investigator agrees to obtain approval from the Sponsor of any written informed consent form used in the study, preferably prior to submission to the IRB or EC.

Once the appropriate essential information has been provided to the subject and fully explained by the investigators (or a qualified designee) and it is felt that the subject understands the implications of participating, the subject and the investigator (or designee) shall sign the IRB- or EC-approved written informed consent form. The subject shall be given a copy of the signed informed consent form, and the original shall be filed appropriately, according to the institution. A second copy may be filed in the subject's medical record, if allowed by the institution.

13.2 Institutional Review Board/Ethics Committee

This protocol, the written informed consent form and any materials presented to subjects shall be submitted to the IRB or EC identified with this responsibility. Notification in writing of approval must come from the IRB or EC chairman or secretary, to the investigator, either as a letter or as a copy of the appropriate section of the IRB or EC meeting minutes where this protocol and associated informed consent form were discussed. The investigator will not participate in the decision. If the investigator is an IRB or EC member, the written approval must indicate such nonparticipation in the voting session. The investigator will submit status reports to the IRB or EC as required by the governing body. The IRB or EC must be notified by the investigator in writing of the interruption and/or completion of the study; the investigator must promptly report to the IRB or EC all changes in research (protocol amendments) and will not make such changes without IRB or EC approval, except where necessary to eliminate apparent immediate hazards to human subjects. In cases where it is necessary to eliminate immediate hazards to subjects, the IRB or EC must then be notified of the change as per local requirements. The investigator is required to maintain an accurate and complete record of all written correspondence to and received from the IRB or EC and must agree to share all such documents and reports with the Sponsor.

14 Confidentiality

All information generated in this study must be considered highly confidential and must not be disclosed to any persons not directly concerned with the study. However, authorized regulatory officials and Sponsor personnel will be allowed full access to the records. All medications provided and subject bodily fluids and/or other materials collected shall be used solely in accordance with this protocol.

Only unique subject numbers in eCRFs will identify subjects. Their full names may, however, be made known to a product regulatory agency or other authorized official if necessary.

Appendix A: Simon Broome diagnostic criteria for Familial Hypercholesterolemia

Definite Familial Hypercholesterolemia:

Required laboratory = high cholesterol levels:

- Adult = Total cholesterol levels > 290 mg/dL (7.5 mmol/L) or LDL-C > 190 mg/dL (4.9 mmol/L)
- Child less than 16 years of age = Total cholesterol levels > 260 mg/dL (6.7 mmol/L) or LDL-C > 155 mg/dL (4.0 mmol/L)

Plus at least one of the two:

1. Plus physical finding = tendon xanthomas, or tendon xanthomas in first or second degree relative

OR

2. DNA-based evidence of an LDL-receptor mutation, familial defective Apo-B-100, or a PCSK9 mutation

Possible Familial Hypercholesterolemia:

Laboratory - high cholesterol levels:

- Adult = Total cholesterol levels > 290 mg/dL (7.5 mmol/L) or LDL-C > 190 mg/dL (4.9 mmol/L)
- Child less than 16 years of age = Total cholesterol levels > 260 mg/dL (6.7 mmol/L) or LDL-C > 155 mg/dL (4.0 mmol/L)

Plus at least one of the two:

1. Family history of at least one of the following.
 - a. Family history of myocardial infarction at:
 - i. Age 60 years or younger in first-degree relative
 - ii. Age 50 years or younger in second-degree relative
2. Family history of elevated total cholesterol
 - a. Greater than 290 mg/dL (7.5 mmol/L) in adult first- or second-degree relative
 - b. Greater than 260 mg/dL (6.7 mmol/L) in child, brother or sister aged younger than 16 years

Source: Austin, et al, 2004.

Appendix B: Requirements for background lipid lowering treatment

There should be no plans at the time of screening and randomization to modify the dose of statin or other lipid lowering medication such as ezetimibe for the duration of the trial. Unless the background lipid lowering treatment exceptions described below are met, subjects must have been treated with one of the following highly effective statins at the specified daily doses and at a stable dose, preferably for 6 weeks but for at least 30 days, prior to screening for the study:

1. atorvastatin, 40 or 80 milligrams (mg) once a day;
2. rosuvastatin, 20 or 40 mg, once a day;
3. simvastatin 40 mg, once a day or, if a subject has been on that dose for >1 year, 80 mg, once a day.

Combination medications that contain atorvastatin, rosuvastatin, or simvastatin components described at the aforementioned doses will be permitted.

Background lipid lowering treatment exceptions

The following background lipid lowering treatment exceptions are permitted:

1. Lower doses of statins due to partial statin intolerance:

Subjects may be on a lower dose of one of the highly effective statins described above if there is documented intolerance to any one of them (atorvastatin, rosuvastatin, or simvastatin) at the aforementioned doses. Intolerance to any dose of any statin must be documented as historical adverse events attributed to the statin in question, in the source documentation and eCRF.

2. Regulatory limitations:

Subjects may be on a lower dose of one of the highly effective statins described above if the highest locally approved dose for one of the stated statins is lower than those doses shown above (eg, in some countries, atorvastatin 20 mg, once a day, is the highest locally approved dose).

3. Alternative statins:

Subjects may be treated with other statins (pravastatin, fluvastatin, pitavastatin, or lovastatin), different from the highly effective statins listed above, if there is documented intolerance to any two different highly effective statins (atorvastatin, rosuvastatin, simvastatin) at the lowest available daily dose for at least one of those highly effective statins. Intolerance to any statin must be documented as historical adverse events attributed to the statin in question, in the source documentation and eCRF.

4. No background statin therapy:

Subjects may be enrolled who are only on nonstatin lipid lowering therapy, if complete statin intolerance has been documented. Subjects with complete statin intolerance must be unable to tolerate at least two statins: one statin at the lowest available daily dose AND another statin at any dose. Intolerance to any statin must be documented as historical adverse events attributed to the statin in question, in the source documentation and eCRF. The sole exception, for which a subject may participate in the study with documentation of intolerance to only one statin, is a documented history of rhabdomyolysis attributed to that statin.

Appendix C: Recommended Neurological Examination

Motor Function

When assessing motor function, from a neurological perspective, the assessment should focus on arm and leg movement. You should consider the following:

1. Muscle size
2. Muscle tone
3. Muscle strength
4. Involuntary movements
5. Posture, gait

Symmetry is the most important consideration when identifying focal findings. Compare one side of the body to the other when performing your assessment.

Assessment of a Conscious Patient

Limb assessment of a conscious patient usually involves a grading of strength.

Grade Strength

Grade strength	Description
5	Full range of motion against gravity and resistance; normal muscle strength
4	Full range of motion against gravity and a moderate amount of resistance; slight weakness
3	Full range of motion against gravity only, moderate muscle weakness
2	Full range of motion when gravity is eliminated, severe weakness
1	A weak muscle contraction is palpated, but no movement is noted, very severe weakness
0	Complete paralysis

NB: In a conscious patient, the single best test to quickly identify motor weakness is the “drift test”. Have the patient hold their arms outward at 90 degrees from the body. With palms up, have the patient close their eyes and hold the arms for a couple of minutes. “Drifting” will occur if one side is weak.

Lower Extremities

Assess the patient in a supine position. Ask him/her to separate both legs to test for hip abduction. Then ask the patient to bring the legs back together to test for hip adduction. Sit the patient on the side of the bed to assess knee flexion and extension. Ask the patient to flex and extend the knee. If able to do this, apply resistance as these movements are repeated. Test plantar and dorsiflexion by having the patient push down against your hand with their foot and then pull up against your hand with their foot. Remember to compare the left side to the right side.

Upper Extremities

Assess ability to flex elbow (biceps) and straighten (triceps). Assess ability to raise shoulders and return to a resting position. Assess wrist flexion and extension. Test each function with resistance. For focused upper extremity assessment, assess each digit for flexion, extension and lateral movement.

Assessment of an Unconscious Patient

Upper Extremities

1. Observe the patient for spontaneous/involuntary movement.
2. Apply painful stimuli to elicit a motor response (start with central pain; move to peripheral pain if no response occurs).
3. Assess for paralysis of the limb by lifting both arms and releasing them together. If one limb is paralysed it will fall more rapidly than the non paralysed arm.

Lower Extremities

1. Observe for spontaneous/involuntary movement.
2. Apply painful stimuli to elicit a motor response. Begin with central pain. Nailbed or peripheral pain can be attempted if the patient doesn't respond to central pain (caution needs to be used when interpreting peripheral pain as it may stimulate spinal reflex responses vs withdrawal or other more deliberate responses).
3. To assess for paralysis of the one limb you can position the patient on their back and flex the knees so that both feet are flat on the bed. Release the knees simultaneously. If the leg falls to an extended position with the hip externally rotated, paralysis is present. The normal leg should stay in the flexed position for a few seconds and then gradually assume its previous position.

Sensory Function

When assessing sensory function remember that there are three main pathways for sensation and they should be compared bilaterally:

1. Pain and temperature sensation.
2. Position sense (proprioception).
3. Light touch.

Pain can be assessed using a sterile pin. Light touch can be assessed with a cotton wisp. To test proprioception, grasp the patient's index finger from the middle joint and move it side to side and up and down. Have the patient identify the direction of movement. Repeat this using the great toe.

Sensory Tests:

A number of tests for lesions of the sensory cortex can be done. Examples include the following:

- **Stereognosis:** The ability to recognize an object by feel. Place a common object in the persons hand and ask them to identify the object.

- **Graphesthesia:** “Draw” a number in the palm of the person’s hand and ask them to identify the number.
- **Two-Point Discrimination:** Simultaneously apply two pin pricks to the skin surface. Continually repeat the test while bringing the two pins closer together, until the individual can no longer identify two separate stimuli. The finger tips are the most sensitive location for recognizing two point differences while the upper arms, thighs and back are the least sensitive.
- **Extinction:** Touch the same spot on both sides of the body at the same time (eg, the left and right forearms. Ask the individual to describe how many spots are being touched. Normally, both sides are felt; with sensory lesions the individual will sense only one.
- **Point Locations:** Touch the surface of the skin and remove the stimulus quickly. Ask the individual to touch the spot where the sensation was felt. Sensory lesions can impair accurate identification, even if they retain their sensation of light touch.

Tone and Reflexes

Upper motor neuron problems (brain and spinal cord) are associated with increased tone. Lower motor neuron problems are associated with decreased tone.

Look at the muscles on each side of the body in pairs. Assess for symmetry of bulk.

Evaluation of the stretch reflexes assesses the intactness of the spinal reflex arc at various spinal cord levels. The limb should be relaxed while applying a short and snappy blow with a reflex hammer. Hold the hammer loosely in a relaxed manner, making a wrist action. Allow the hammer to bounce.

Reflex responses:

0	No response
1+	Diminished, low normal
2+	Average, normal
3+	Brisker than normal
4+	Very brisk, hyperactive

Lower motor neuron disease is associated with 0 or 1+, upper motor neuron disease is associated with 3+ or 4+.

Biceps Reflex (C5 – C6):

Support the forearm on the examiners forearm. Place your thumb on the bicep tendon (located in the front of the bend of the elbow; midline to the antecubital fossa). Tap on your thumb to stimulate a response.

Triceps Reflex (C7-C8):

Have the individual bend their elbow while pointing their arm downward at 90 degrees. Support the upper arm so that the arm hangs loosely and “goes dead”. Tap on the triceps tendon located just above the elbow bend (funny bone).

Brachioradialis Reflex (C5-C6):

Hold the person's thumb so that the forearm relaxes. Strike the forearm about 2-3 cm above the radial styloid process (located along the thumb side of the wrist, about 2-3 cm above the round bone at the bend of the wrist). Normally, the forearm will flex and supinate.

Quadriceps Reflex (Knee jerk) L2 - L4:

Allow the lower legs to dangle freely. Place one hand on the quadriceps. Strike just below the knee cap. The lower leg normally will extend and the quadriceps will contract.

If the patient is supine: Stand on one side of the bed. Place the examiner's forearm under the thigh closest to the examiner, lifting the leg up. Reach under the thigh and place the hand on the thigh of the opposite leg, just above the knee cap. Tap the knee closest to the examiner, (the one that has been lifted up with the examiner's forearm).

Achilles Reflex (ankle jerks) L5 - S2:

Flex the knee and externally rotate the hip. Dorsiflex the foot and strike the Achilles tendon of the heel. In conscious patients, kneeling on a chair can help to relax the foot.

Heel Lift:

While the patient is supine, bend the knee and support the leg under the thigh. Have the leg "go dead". Briskly jerk the leg to lift the heel of the bed. Normally, the leg will remain relaxed and the heel will slide upward; increased tone will cause the heel and leg to stiffen and lift off the bed.

Babinski Response:

Dorsiflexion of the great toe with fanning of remaining toes is a positive Babinski response. This indicates upper motor neuron disease. It is normal in infants.

Cerebellar Function

The cerebellum is responsible for muscle coordination and balance on the same side. To test cerebellar function use the following tests:

1. Finger to finger test: have the patient touch their index finger to your index finger (repeat several times).
2. Finger to nose test: perform with eyes open and then eyes closed.
3. Tandem walking: heel to toe on a straight line.
4. Romberg test: stand with feet together and arms at their sides. Have patient close his/her eyes and maintain this position for 10 seconds. If the patient begins to sway, have them open their eyes. If swaying continues, the test is "positive" or suggestive of cerebellum problems.

Dizziness that occurs in response to position changes is usually blood pressure initiated. If the patient sways during a Romberg test, but stops when the eyes are opened, the problem is probably visual or CN VIII (vestibular).

Appendix D: Sampson Criteria for Diagnosing Anaphylaxis

Anaphylaxis is highly likely when any one of the following three criteria is fulfilled:

1. Acute onset of an illness (minutes to several hours) with involvement of the skin, mucosal tissue, or both (eg, generalized hives, pruritus or flushing, swollen lips-tongue-uvula)

AND AT LEAST ONE OF THE FOLLOWING:

- a. Respiratory compromise (eg, dyspnea, wheeze-bronchospasm, stridor, reduced peak expiratory flow [PEF], hypoxemia)
- b. Reduced blood pressure or associated symptoms of end-organ dysfunction (eg, hypotonia [collapse], syncope, incontinence)

2. Two or more of the following that occur rapidly after exposure to a likely allergen for that patient (minutes to several hours):
 - a. Involvement of the skin-mucosal tissue (eg, generalized hives, itch-flush, swollen lips-tongue-uvula)
 - b. Respiratory compromise (eg, dyspnea, wheeze, bronchospasm, stridor, reduced PEF, hypoxemia)
 - c. Reduced blood pressure or associated symptoms (eg, hypotonia [collapse], syncope, incontinence)
 - d. Persistent gastrointestinal symptoms (eg, painful abdominal cramps, vomiting)
3. Reduced blood pressure after exposure to a known allergen for that patient (minutes to several hours):
 - a. Infants and children: low systolic blood pressure (age specific) or >30% decrease in systolic blood pressure*
 - b. Adults: systolic blood pressure <90 millimeters of mercury (mmHg) or >30% decrease from that person's Day 1 reading

*Low systolic blood pressure for children is age specific and defined as: <70 mmHg from age 1 month to 1 year; <70 mmHg + [2 x age] for age 1 to 10 years; <90 mmHg from age 11 to 17 years.

Source: Sampson *et al*, 2005; Sampson *et al*, 2006.

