4.5 Stopping Criteria

4.5.1 Individual Subject Dosing Stopping Criteria

During the study subjects will have clinic visits at regular intervals. Dosing with study medication (inclisiran and/or matching placebo) should be temporarily discontinued or stopped in subjects with:

1. Intolerable adverse events, or if the Investigator believes that continuing dosing will be detrimental to the subject's mental or physical health. This includes severe or serious reactions at the injection site and any anaphylactic type reactions.
2. Unexplained increases in transaminases (ALT or AST) or total bilirubin as follows:
 - a. ALT or AST >8xULN
 - b. ALT or AST >5xULN for more than 2 weeks
 - c. ALT or AST >3xULN and (total bilirubin >2xULN or INR >1.5)
 - d. ALT or AST >3xULN with the appearance of fatigue, nausea, vomiting, right upper quadrant pain or tenderness, fever, rash, and/or eosinophilia (>5%)

The investigator should evaluate to see if other causes for the laboratory abnormalities are immediately apparent, such as obstructive gall bladder or bile duct disease, viral or alcoholic hepatitis, malignancy involving the liver, congestive hepatopathy, other hepatotoxins or heritable disorders.

3. Unexplained creatine kinase (CK) values >5 x ULN confirmed by repeat test when the CK elevation is associated with muscle pain, muscle tenderness and/or muscle weakness, or new onset renal dysfunction.

In the case that study medication is permanently discontinued the subject will be asked to complete the remainder of the scheduled visits without receiving study medication (inclisiran or placebo).

All trial subjects should be followed until all abnormalities return to normal or to the baseline state.

5 Treatment of Subjects

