5.2.2 Permitted Concomitant Medications

The following medications/treatments are permitted during the study:

- Hormone replacement therapy
- Lipid-lowering medications; subjects already on a stable (≥ 30 days before screening) lipid-lowering medications (such as statins and/or ezetimibe) should remain on the dose that they have received at time of study entry
- Prescription medications prescribed to treat preexisting medical conditions such as diabetes and hypertension

- Prescription or nonprescription medications, when necessary to treat an AE, and at the discretion of the investigator

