6.6 Additional Dosing Visits (Days 90, 180, 270, 450, and 630)

Subjects will return on Day 90 for a second investigational product injection. Subsequent inclisiran injections will be administered to all subjects on Day 270, Day 450 and Day 630. In addition, on Day 180 subjects originally randomized to the placebo group will be switched to inclisiran and receive their first dose of inclisiran on Day 180.

Note: For subjects randomized to the inclisiran arm, Day 180 will be a non-dosing visit but the same assessments as described below will be performed except for investigational product administration.

The following assessments will be completed during these visits prior to investigational product administration:

- Pregnancy test (performed locally, prior to any dosing, using central laboratory supplies, if applicable) (women of childbearing potential only)
- Vital signs: blood pressure and heart rate ([Section 7.1.3](#))
- Fasting lipid profile/biomarkers ([Section 7.2](#))
- Assessment of ADA (Day 90 only) ([Section 7.1.7.8](#))
- Central clinical laboratory (limited serum chemistry) ([Section 7.1.7](#))
- Concomitant medication
- AE/SAE reporting

Administration of the investigational product is identical to Day 1 and is per [Section 5.1.1](#) and the Pharmacy Manual.

Subjects must be observed in the clinic for at least 30 minutes after injection.

Should a subject develop signs or symptoms of anaphylaxis on days when investigational product is injected, the investigator will need to collect a blood sample for tryptase within 30 minutes of the onset of anaphylaxis (or as soon as logically possible).

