8.3.2 Other safety related information

Injection-site reactions including individual signs or symptoms at the injection site following investigational product administration should be recorded on specifically designed eCRF pages. Photographs of injection-site reactions, if they were obtained during the study visits, should be forwarded to study inbox.

Other safety related information that should be reported as adverse events in accordance with the process described in [Section 8.4](#) include:

- Abnormal neurological examination, eg, peripheral sensory and motor evaluation, an assessment of gait, pain, position, strength and reflexes ([Appendix°C](#)).
- Potential anaphylactic reactions assessed by Sampson criteria ([Appendix°D](#)). If Sampson criteria are positive, confirm by elevation of tryptase in blood plasma measured within 30 minutes of symptoms.
- Hyperglycemia-related AEs:
 - Report 'New onset of diabetes' in subjects with no medical history of diabetes when:
 - HbA1C becomes $\geq 6.5\%$ and/or
 - Two consecutive values of fasting plasma glucose that are ≥ 126 mg/dL
 - If a new concomitant medication for control of plasma glucose is added, further information to assess for a diagnosis of new onset diabetes will be collected.
 - Report 'Worsening of the glycemic control' or 'diabetic complications' in subjects with a medical history of disease (HbA1C $\geq 6.5\%$ at baseline) when:
 - HbA1C increases from baseline $> 0.5\%$ and/or
 - New concomitant medication or increase in dose of current antidiabetic therapy is initiated to improve the control of plasma glucose level.

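### Appendix D item 3b measures an adult's post-injection fall in blood pressure from the Day 1 reading, although a pre-injection reading is taken at every later dosing visit

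*Protocol*

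**What the plan says.** Protocol Section 8.3.2 lists among the events to be reported as adverse events "Potential anaphylactic reactions assessed by Sampson criteria", and asks that a positive result be followed up: "confirm by elevation of tryptase in blood plasma measured within 30 minutes of symptoms". The criteria are in Appendix D.

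- Criterion 3 begins "Reduced blood pressure after exposure to a known allergen for that patient (minutes to several hours", and its adult item 3b reads "Adults: systolic blood pressure <90 millimeters of mercury (mmHg) or >30% decrease from that person's Day 1 reading". This is the appendix's only numeric definition of reduced blood pressure for adults.
- Criteria 1 and 2 each require at least one further feature. Their blood-pressure items carry no adult threshold and also accept symptoms. Item 2c, for example, reads "Reduced blood pressure or associated symptoms (eg, hypotonia [collapse], syncope, incontinence".

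Under Section 3.1 the inclisiran arm is injected on Days 1, 90, 270, 450 and 630. Former placebo subjects receive inclisiran on Days 180, 270, 450 and 630. Section 6.6 introduces its list for the later dosing visits with "The following assessments will be completed during these visits prior to investigational product administration", and blood pressure is on that list. Section 6.4 places the Day 1 vital signs before the injection as well.

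**The concern.** A fall caused by an injection has to be measured from the state just before that injection. On Day 1 the reference in item 3b is such a reading. At every later dosing visit it is months old, and any change in pressure over those months is mixed into the apparent reaction. Pressure that has risen since Day 1 can hide a real fall. Pressure that has dropped since Day 1 can make a small dip count as a large one.

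Day 1 pressure need not persist. Section 4.3 admits subjects with systolic pressure up to 180 mmHg. Section 5.2.2 permits "Prescription medications prescribed to treat preexisting medical conditions such as diabetes and hypertension" and sets no stability requirement for them, whereas Section 5.2.1 requires lipid-lowering treatment to stay stable.

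At stake is whether a suspected hypersensitivity event is labelled as meeting the anaphylaxis criteria, in a study whose objectives include safety and tolerability. Section 12 of the amendment record aside, the Amendment 1 rationale gives 56 subjects enrolled, so one event moves the reported proportion by 1/56 = 1.8 percentage points.

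**Working it through.** The protocol gives no figure on this point, so there is none to reproduce.

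**Step 1. How many injections have an old reference.** Inputs: at least 45 subjects at 2:1, hence 30:15 (Sections 4.1 and 10.1), and the dosing days in Section 3.1.

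- Inclisiran arm: 30 × 5 = 150 injections, of which 30 fall on Day 1.
- Former placebo subjects: 15 × 4 = 60 inclisiran injections, none on Day 1.
- Total: 150 + 60 = 210. After Day 1: 210 − 30 = 180, and 180/210 = 85.7%.
- For the 56 actually enrolled, assuming a 37:19 split: 37 × 5 + 19 × 4 = 261. After Day 1: 261 − 37 = 224, and 224/261 = 85.8%.
- Age of the reference: Day 90 to Day 630, or 90/30 = 3 to 630/30 = 21 months. For former placebo subjects it is at least 6 months, starting at Day 180.

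**Step 2. Where the choice of reference matters.** With reference pressure R, item 3b is met when post-injection systolic pressure lies below max(90, 0.7 × R). The relative limb exceeds 90 only if R > 90/0.7 = 128.6 mmHg. It follows that:

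- a Day 1 reading of about 128 or lower makes the Day 1 limb redundant;
- a fall can be missed only if the pre-dose reading is above both 128.6 and the Day 1 reading;
- a fall can be wrongly counted only if the Day 1 reading is above both 128.6 and the pre-dose reading;
- a post-injection value below 90 is classified the same way under either reference.

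**Step 3. Illustrations.** The pressures in mmHg are assumed, because the protocol gives none.

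| Day 1 | Pre-dose | Limit from Day 1 | Limit from pre-dose | Consequence |
|---|---|---|---|---|
| 120 | 160 | max(90, 84) = 90 | max(90, 112) = 112 | 90 to below 112 not counted |
| 130 | 150 | max(90, 91) = 91 | max(90, 105) = 105 | 91 to below 105 not counted |
| 150 | 130 | max(90, 105) = 105 | max(90, 91) = 91 | 91 to below 105 counted |
| 170 | 125 | max(90, 119) = 119 | max(90, 87.5) = 90 | 90 to below 119 counted |

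In the first row, a post-dose value of 95 is an acute fall of 1 − 95/160 = 40.6%, yet it meets neither limb. In the last row, the Day 1 limb is met once pressure drops below 119, a fall of 1 − 119/125 = 4.8%.

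**The case against.** Much can be said for leaving the text alone, and most of it narrows the point.

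- **The absolute limb.** A reader might infer that the whole adult definition hangs on Day 1, or that 86% of injections are misjudged. Neither follows. The limb at 90 mmHg is independent of Day 1, and 86% counts injections after Day 1, not errors.
- **Known allergen.** Item 3b decides alone only under criterion 3. Section 4.3 excludes subjects hypersensitive to any ingredient of inclisiran. Section 4.5.1 has dosing interrupted or stopped for intolerable events and adds: "This includes severe or serious reactions at the injection site and any anaphylactic type reactions". A fall in pressure alone would therefore rarely settle the label.
- **Criteria 1 and 2.** It is tempting to carry the number in 3b into items 1b and 2c. The appendix does not do so expressly, and both items can be met by symptoms without any reading.
- **Pre-dose values.** A low reading before the injection cannot itself meet criterion 3, which concerns pressure after exposure. Section 7.1.3 requires one blood-pressure assessment per visit, so a post-injection value would normally exist only because a reaction was already suspected.
- **Downstream decisions.** A reader might infer that item 3b drives tryptase sampling or dosing. Sections 6.4 and 6.6 trigger the sample on clinical signs or symptoms. Section 4.5.1 does not cite Appendix D and leaves room for investigator judgment. Section 8.4.2 records non-serious events whatever their cause.

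All of this limits how often the wording matters. None of it makes a reading 3 to 21 months old a sound reference for a fall within hours of an injection. Tryptase confirmation of positives under Section 8.3.2 can also correct a false label but not restore a missed one.

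**Conclusion.** The point holds in a narrow form and is minor. The relative limb of item 3b uses a reference that does not fit the acute event it describes at about 86% of planned inclisiran injections. It can misclassify in both directions, but only when post-injection systolic pressure is 90 mmHg or more and the Day 1 and pre-dose readings differ enough to move the limit.

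The count of 180 of 210 rests on full dosing at 30:15, and the illustrative pressures are assumptions. No misclassification rate can be given. The protocol reports no blood-pressure distribution, and any simulated percentage would depend on invented means and standard deviations and would treat blood pressure as decisive by itself. The consequence is confined to the label of a rare safety event under Section 8.3.2. The primary and secondary efficacy analyses are untouched.

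**What to change.** Reconcile Appendix D item 3b with Sections 6.4 and 6.6, so that for safety classification the post-injection fall is referred to the pre-injection reading already collected at that dosing visit. State whether the same reference applies to reduced blood pressure in items 1b and 2c. Leave every percentage and mmHg threshold, and every dosing rule, as it stands.

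The cost is one phrase in the appendix and the matching line in the safety data handling. No visit, measurement or subject is added. The small downside is that any event after Day 1 that has already been classified needs one re-check against the same-visit reading.
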